### INDEX.

Condition or disease  
Toxocariasis  
Ocular Toxocariasis  
Pulmonary Toxocariasis  
Ground Glass Opacity (GGO)  
Toxocara Canis Infection (Canine Roundworms)  
Law Liver  
Law Meat  
Serum Toxocara Antibody  
Toxocara Larva Migrans

## Study Description

### Brief Summary:

TOXOCARA Study is a prospective observational cohort study. The aim of this study is to evaluate the incidence of ocular toxocariasis (OT) associated with pulmonary toxocariasis (PT) in patients who were diagnosed by chest diagnostic image tests (chest X-ray, chest CT) with migrating ground glass opacity or nodular lesions. Also a cohort study is to track the results of treatment for diagnosed ocular toxocariasis (OT) patients.

### Detailed Description:

*Toxocara canis* (also known as dog roundworm) is wide-reaching parasite of dogs and other canids. It can spread between animals such as cats, pigs and cows by ingestion of worm eggs from the feces of an infected animal.

In humans, two pathways of infection are known: first, ingestion of the eggs and second, larvae encapsulated in the tissues of the infected animal.

The encapsulated larvae hatch in the small intestine and pass through the barrier to the portal vein, the liver, the lung, the eye, etc. and remain as encapsulated larvae or survive for a period of time.

Infection into humans has been reported through ingestion of uncooked liver of cows, pigs, sheep, chickens, and meat (muscle).

When encapsulated larvae migrate to the body such as lungs, eosinophils activate and proliferate to eliminate the parasites.

They can be expressed as ground glass opacity (GGO) or nodular lesion by aggregated eosinophils, which are mistaken for lung cancer or pneumonia to be investigated.

Asthma exacerbation, cough and other symptoms of respiratory system could be revealed, but often asymptomatic.

In this study, the investigators defined pulmonary toxocariasis (PT) as a positive form of serum toxocara Ab and migrating pulmonary GGOs or nodular lesions in chest diagnostic image tests (chest X-ray, chest CT) from the patient.

Approved by Ulsan University Hospital IRB	Valid from: July 10, 2017	through July 31, 2020	IRB#: UUH 2017-06-012-001
Brief Study Title: A Study for the Ocular Toxocariasis in the Patients Who Were Diagnosed With the Pulmonary Toxocariasis, and Ocular Toxocariasis Cohort			

Also ocular toxocariasis (OT) is defined by the clinical manifestation of intraocular infection by *Toxocara* larvae with a positive result of serum toxocara Ab.

Clinical manifestations of OT may also cause blindness of peripheral granuloma, optic neuritis, chorioretinitis, conjunctivitis, keratitis, iridocyclitis and cataract.

The investigators want to investigate the incidence of OT associated with PT in patients with chest diagnostic image tests (chest X-ray, chest CT) with migrating GGOs or nodular lesions. Also a cohort study is to track the results of treatment for diagnosed OT patients.

## SAMPLE SIZE

Estimated Enrollment: 400 participants

Observational Model: Cohort

Time Perspective: Prospective

Target Follow-Up Duration: 3 Years

In a preliminary study, one case of ocular toxocariasis (OT) among 12 cases of pulmonary toxocariasis (PT) was diagnosed (about 8%).

Based on this, the investigators aimed at 400 pulmonary toxocariasis (PT): 32 ocular toxocariasis (OT).

### Statistical analysis

All analyses in this study will be pre-specified. Statistical analysis will be performed using SPSS 21 and Graphpad PRISM 6.0. The results will be expressed as means  $\pm$  SE. Summary data will be reported as mean  $\pm$  SEM. Statistical significance will be confirmed at a p value of  $<0.05$ .

Parametric statistical tests: Student T-test, paired t- test, One-way ANOVA, Fisher's exact test, Chi-square

Non-parametric statistical tests: Mann-Whitney U test, Wilcoxon signed rank test

: simple linear regression, multiple regression analysis

### Predictive side effects and precautions for the study

In the present study, blood tests such as CBC, eosinophil count, toxocara Ab, and ocular examinations for screening purposes will be generally performed.

The results of this study suggest that there is no additional side effect because it is a common blood test and ocular examination.

Approved by Ulsan University Hospital IRB	Valid from: July 10, 2017 through July 31, 2020	IRB#: UUH 2017-06-012-001
Brief Study Title: A Study for the Ocular Toxocariasis in the Patients Who Were Diagnosed With the Pulmonary Toxocariasis, and Ocular Toxocariasis Cohort		

Consideration of the safety of the subjects (test suspension, serious adverse reaction / countermeasures for adverse reactions, etc.)

Although there is no additional side effect of this study, if the adverse reaction occurs, it will be stopped immediately. The investigator will notify the patient immediately.

How to secure research ethics

All the investigators will strictly observe the Declaration of Helsinki, Ethical Principles for Medical Research Involving Human Subjects, which defines the specific purpose, method and ethics of medical research.

All the investigators participating in this study will comply with the measures necessary for securing the ethics of this study, that is, to guarantee autonomy of patient participation, to provide sufficient explanation, to guarantee full withdrawal and to prohibit the privacy of patients.

## Study Design

Study Type: Observational (cross sectional, cohort)  
 Estimated Enrollment: 400 participants  
 Observational Model: Cohort  
 Time Perspective: Prospective  
 Target Follow-Up Duration: 3 Years

Actual Study Start Date: July 10, 2017  
 Estimated Primary Completion Date: July 31, 2020  
 Estimated Study Completion Date: July 31, 2020

## Outcome Measures

- 1) Primary Outcome Measure: Number of patients with pulmonary toxocariasis (PT) [Time Frame: at baseline]
- Patients who have a positive result of serum toxocara Ab and migrating pulmonary GGOs or nodular lesions and history of eating of law animal liver or meat or history of having the pets such as dogs and cats.

Approved by Ulsan University Hospital IRB	Valid from: July 10, 2017	through July 31, 2020	IRB#: UUH 2017-06-012-001
Brief Study Title: A Study for the Ocular Toxocariasis in the Patients Who Were Diagnosed With the Pulmonary Toxocariasis, and Ocular Toxocariasis Cohort			

- 2) Number of patients with ocular toxocariasis (OT) [Time Frame: at baseline]
  - Patients who have the clinical manifestation of intraocular infection by Toxocara larvae and a positive result of serum toxocara Ab and history of eating of law animal liver or meat. (and/or migrating pulmonary GGOs or nodular lesions) or history of having the pets such as dogs and cats.
  
- 3) Number of patients with ocular toxocariasis (OT) among the patients with pulmonary toxocariasis (PT), [Time Frame: at baseline]
  - Patients who have ocular toxocariasis (OT) with pulmonary toxocariasis (PT)

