### Study Population

- 1) The investigators defined pulmonary toxocariasis (PT) as a positive form of serum toxocara Ab and migrating pulmonary GGOs or nodular lesions in chest diagnostic image tests (chest X-ray, chest CT) from the patient.
- 2) Ocular toxocariasis (OT) is defined by the clinical manifestation of intraocular infection by Toxocara larvae and a positive form of serum toxocara Ab.

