### Criteria

#### Inclusion Criteria:

- 1) Aged 18 years and older
- 2) Patient who has positive result of Toxocara Ab
- 3) Patient who has history of eating of law animal liver or meat
- 4) Patient who has the chest diagnostic image tests (chest X-ray, chest CT) with migrating ground glass opacity or nodular lesions.

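### The count of ocular toxocariasis among pulmonary toxocariasis patients (outcome 3) has no rule on how patients entered, so anyone whose chest was imaged because of eye disease would push it upward

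*Combined protocol and SAP*

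**What the plan says.** All references are to the combined protocol and SAP.

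- **Aim.** The Brief Summary and Detailed Description set out to find how often OT occurs in patients with migrating ground glass or nodular lesions on chest X-ray or CT. The Brief Summary adds a second component: "Also a cohort study is to track the results of treatment for diagnosed ocular toxocariasis (OT) patients".
- **Outcome 3.** Under Outcome Measures it is "Number of patients with ocular toxocariasis (OT) among the patients with pulmonary toxocariasis (PT), [Time Frame: at baseline", explained only as "Patients who have ocular toxocariasis (OT) with pulmonary toxocariasis (PT".
- **Outcome 2.** The count of all OT patients treats lung findings as optional: "and/or migrating pulmonary GGOs or nodular lesions".
- **Definition of OT.** Study Population does not refer to the chest: "Ocular toxocariasis (OT) is defined by the clinical manifestation of intraocular infection by Toxocara larvae and a positive form of serum toxocara Ab".
- **Inclusion.** Age 18 or over, positive antibody, a history of eating raw liver or meat, and "Patient who has the chest diagnostic image tests (chest X-ray, chest CT) with migrating ground glass opacity or nodular lesions".
- **Exclusion.** Six items: age under 18, pregnancy, malignancy, infectious lung lesions, diagnosed pulmonary nodule, and no consent. None concerns OT or the reason for imaging.
- **Sample Size.** "the investigators aimed at 400 pulmonary toxocariasis (PT): 32 ocular toxocariasis (OT", based on one OT case among 12 PT cases in a preliminary study.
- **Follow-up.** Secondary outcome 6 follows OT patients for 3 years after treatment. No section says where those patients come from.
- **Analysis.** The Statistical analysis section names tests and software. It has no restriction or breakdown by route of entry.

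**The concern.** A proportion of PT patients with OT is interpretable only if having OT did not itself bring patients into the denominator. The aim implies entry through the chest finding. The operative rules require only that lesions are present; they do not ask why anyone looked for them.

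Take a patient with known OT who is seropositive, has eaten raw liver or meat, and has a chest image taken because of the eye disease. If it shows migrating lesions, and no unrelated exclusion applies, the patient is eligible, is a PT case by definition, and is an OT case by the way they were found. Such a patient says nothing about how often chest-identified PT patients have OT, yet adds one to both numerator and denominator.

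The error runs in one direction and does not shrink as enrolment grows. If the reason for imaging is not recorded, the analysis cannot separate these patients afterwards.

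**Working it through.** **Inputs from the plan.** 400 PT patients, 32 expected OT cases, and a preliminary result of 1/12 (Sample Size).

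**Input not in the plan.** The number k of eye-route patients, meaning those whose chest was imaged as work-up of eye disease. It is varied below, and zero is possible.

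**1. The plan's own figure.** 400 × 0.08 = 32.0, which matches. With the unrounded 1/12 it is 400/12 = 33.3. At 32/400 the exact 95% interval is 5.5% to 11.1%, and the normal-approximation half-width is 1.96 × √(0.08 × 0.92 / 400) = 2.7 points.

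**2. Effect of eye-route patients within the 400.** Let f = k/400, and suppose every eye-route patient has confirmed OT. The expected proportion is

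0.08(1 − f) + f = 0.08 + 0.92f.

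| k of 400 | f | Expected proportion | Shift (points) |
|---|---|---|---|
| 0 | 0 | 8.0% | 0 |
| 10 | 2.5% | 10.3% | 2.3 |
| 12 | 3% | 10.8% | 2.8 |
| 20 | 5% | 12.6% | 4.6 |
| 40 | 10% | 17.2% | 9.2 |

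At k = 12 the shift slightly exceeds the sampling half-width. At k = 13 the expected count is 387 × 0.08 + 13 = 43.96, or about 44/400 = 11.0%. Its exact 95% interval, 8.1% to 14.5%, no longer contains the assumed 8%.

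**3. If only suspected OT prompted the imaging.** Some of these patients may not prove to have OT. If a fraction q do, the shift is f(q − 0.08). It is upward whenever q exceeds 0.08, and 0.92f is the upper limit. The table is therefore the worst case for each k.

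**4. Extra patients instead of replacements.** If eye-route patients are added to the 400, the proportion is (32 + k)/(400 + k). For k = 16 this is 48/416 = 11.5%, against 11.7% from step 2.

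**5. Read backwards.** Suppose 32/400 is observed. If 8, 16 or 24 of the 32 were eye-route, the chest-route proportion would be 24/392 = 6.1%, 16/384 = 4.2% or 8/376 = 2.1%. Likewise, a chest-route proportion of 4% with 16 eye-route patients gives (384 × 0.04 + 16)/400 = 7.8%, close to the planned 8%. Agreement with the planned figure would not show that the problem is absent.

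**6. Can the preliminary study serve as a check?** No. The exact 95% interval for 1/12 is 0.2% to 38.5%, and its route of entry is not stated.

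**The case against.** **The intended flow is chest to eye.** The brief study title, the aim and the imaging criterion all point that way. The section on predictive side effects lists blood tests and screening eye examinations among the study procedures, and no chest imaging. No section sends eye patients for chest imaging. There is one enrolment figure, 400, and the 32 OT cases are described as arising among those 400. The simplest reading is that the OT cohort consists of those cases. All of this stands. It establishes intent, but it does not supply a rule: the imaging criterion requires lesions to exist, not to have been found independently of the eye.

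**A stronger reading to resist.** A reader might infer that OT patients will be recruited through eye clinics to fill the treatment cohort or reach 32 cases, and that outcome 3 will therefore be inflated. The documents do not support this. They describe no eye-clinic stream, no separate OT enrolment target and no second site; the only approval shown is one hospital's. Outcome 2 does allow OT without lung lesions, which fits poorly with an inclusion list requiring lesions in everyone. But a patient without lesions is not a PT case and cannot affect outcome 3. That wording shows only that the plan does not confine OT patients to those who came in through the chest.

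**Prior OT is not the same as eye-route entry.** A patient with known OT whose lung lesions turn up on unrelated imaging belongs in outcome 3. Removing everyone with earlier OT would bias the result downward: if 16 of a true 32/400 were such patients, it would report 16/384 = 4.2% instead of 8.0%. This stands, and it is why the fix turns on the reason for imaging and not on which diagnosis came first.

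**Conclusion.** The point holds as a missing operational rule. The plan states a chest-identified population, but nothing in eligibility, outcome 3 or the analysis enforces that route or records departures from it. Any eye-route OT patients enrolled would raise the outcome 3 proportion.

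The size cannot be determined from the documents. It rests on two assumptions: a chest-route proportion of 8%, which comes from a single case among 12, and an unknown k. From k = 0 to 40 of 400 the expected result runs from 8.0% (no bias) to 17.2%, and about 12 such patients would matter as much as sampling error. The change is worth making because it is cheap and an unrecorded reason for imaging cannot be supplied by the analysis.

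**What to change.** 1. **Case-report form.** Add one item, completed at enrolment: was the chest imaging that showed the lesions done independently of eye disease, or as work-up of known or suspected OT?
2. **Outcome Measures, outcome 3.** Define it as the proportion with OT at baseline among PT patients whose lung lesions were found on imaging done independently of eye disease. State that patients with previously known OT are kept if they entered by that route.
3. **OT cohort.** Patients imaged because of OT contribute to secondary outcome 6 and not to the main analysis of outcome 3.
4. **Statistical analysis.** Report the proportion among all PT patients as a sensitivity analysis, with the number in each route.
5. **Consistency.** Reconcile outcome 2, where lung lesions are optional, with the inclusion list, where they are required, and say where OT cohort patients come from.

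**Cost.** One data item and short text changes. Fewer than 32 OT cases may count toward outcome 3. For example, with 40 eye-route patients among 400, the denominator is 360 and the expected OT count is 360 × 0.08 = 28.8. The half-width becomes 1.96 × √(0.08 × 0.92 / 360) = 2.8 points instead of 2.7, so little precision is lost. If no eye-route patients enrol, the result is unchanged.

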#### Secondary Outcome Measures:

- 1) Incidence of Cysticercosis [Time Frame: at baseline]
  - Patient who have a positive result of serum cysticercosis Ab and history of eating of law animal liver or meat. (and/or migrating pulmonary GGOs or nodular lesions)
  
- 2) Incidence of Sparganosis [Time Frame: at baseline]
  - Patient who have a positive result of serum sparganum Ab and history of eating of law animal liver or meat. (and/or migrating pulmonary GGOs or nodular lesions)
  
- 3) Incidence of Clonorchiasis [Time Frame: at baseline]
  - Patient who have a positive result of serum clonorchis sinensis Ab and history of eating of the law freshwater fish or its cuisine. (and/or migrating pulmonary GGOs or nodular lesions)
  
- 4) Incidence of Paragonimiasis [Time Frame: at baseline]
  - Patient who have a positive result of serum paragonimus westermani Ab and history of eating of the law freshwater crabs or crayfish or its cuisine. (and/or migrating pulmonary GGOs or nodular lesions)
  
- 5) Incidence of Anisakiasis [Time Frame: at baseline]

Approved by Ulsan University Hospital IRB	Valid from: July 10, 2017 through July 31, 2020	IRB#: UUH 2017-06-012-001
Brief Study Title: A Study for the Ocular Toxocariasis in the Patients Who Were Diagnosed With the Pulmonary Toxocariasis, and Ocular Toxocariasis Cohort		

- Patient who have a positive result of serum anisakis Ab and history of eating of the law oceanic fish or its cuisine. (and/or migrating pulmonary GGOs or nodular lesions)
- 6) Clinical course of the patients with ocular toxocariasis (OT) after treatment [Time Frame: 3 years]
- Follow-up : ocular toxocariasis cohort (clinical course of the patients with ocular toxocariasis (OT) after treatment by ophthalmologists)

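### The 3-year follow-up of treated ocular toxocariasis patients fits inside a study of 3 years and 21 days only as a maximum, and the plan does not say so

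*Combined protocol and SAP*

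**What the plan says.** The Brief Summary gives the study a second aim beyond counting cases: "Also a cohort study is to track the results of treatment for diagnosed ocular toxocariasis (OT) patients". Item 6 of the Secondary Outcome Measures carries that aim: "Clinical course of the patients with ocular toxocariasis (OT) after treatment [Time Frame: 3 years"]. It is the only outcome with any follow-up. The Sample Size section states "Target Follow-Up Duration: 3 Years", and Study Design repeats it.

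Study Design also fixes the calendar: "Actual Study Start Date: July 10, 2017", "Estimated Primary Completion Date: July 31, 2020" and "Estimated Study Completion Date: July 31, 2020". The IRB validity printed in the page headers covers the same period and ends on the same day. The primary outcomes are all measured at entry, the first being "Number of patients with pulmonary toxocariasis (PT) [Time Frame: at baseline"].

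No section gives an enrolment closing date, a minimum follow-up, a common assessment time for outcome 6, or wording that makes 3 years an upper limit. The Statistical analysis section lists tests and regressions, among them "Non-parametric statistical tests: Mann-Whitney U test, Wilcoxon signed rank test", without tying any of them to outcome 6 or saying how unequal follow-up would be handled.

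**The concern.** A per-patient follow-up of 3 years needs the study to last 3 years beyond the last start of treatment. Here the whole study, from first enrolment to completion, is barely longer than the follow-up alone. Only patients treated almost at once could be followed for the stated time.

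The placing of primary completion sharpens this. The primary outcomes are baseline measurements, yet their completion date is the last day of the study. That suggests enrolment may continue to the end, in which case the shortest follow-up would be close to zero.

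At stake is how the treatment results of the ocular cohort can be read. A result labelled with a 3-year time frame would invite readers to take it as a 3-year clinical course, when few or no patients could supply one. The listed paired tests could be used to compare baseline with last visit, but that comparison would mix patients followed for weeks with patients followed for years.

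**Working it through.** **Inputs.** Start July 10, 2017 and completion July 31, 2020 (Study Design); follow-up of 3 years (Secondary Outcome Measures, item 6; Sample Size; Study Design); 400 pulmonary and 32 ocular cases (Sample Size).

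**The plan's own figure.** The preliminary rate is 1/12 = 8.3%, stated as about 8%. 400 × 0.08 = 32, which reproduces the stated number of ocular cases (the unrounded rate gives 33.3). The point below does not affect this figure.

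**Study length.** July 10, 2017 to July 10, 2020 is 1,096 days. Adding 21 days to July 31, 2020 gives 1,117 days.

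**Window for full follow-up.** 1,117 − 1,096 = 21 days. This assumes that treatment starts within the study, that follow-up is counted from the start of treatment, and that the completion date holds. The latest start that allows 3 years is then July 31, 2017. For every ocular patient to reach 3 years, all 400 participants would have to be enrolled, diagnosed and, where ocular disease is found, treated in those 21 days: 400/21 ≈ 19 enrolments per day.

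**Shares if treatment starts are uniform to July 31, 2020** (a further assumption). Share = day of latest possible start / 1,117; expected patients = share × 32.

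| Follow-up | Latest start | Day | Share | Of 32 |
|---|---|---|---|---|
| 36 months | July 31, 2017 | 21 | 21/1,117 = 1.9% | 0.6 |
| 24 months | July 31, 2018 | 386 | 386/1,117 = 34.6% | 11.1 |
| 12 months | July 31, 2019 | 751 | 751/1,117 = 67.2% | 21.5 |
| 6 months | January 31, 2020 | 935 | 935/1,117 = 83.7% | 26.8 |

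Median possible follow-up = 1,117/2 = 558.5 days, about 18.3 months.

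**Sensitivity to the unstated accrual period.** With uniform starts over a shorter period, the share reaching 3 years is 21 / accrual days:

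- 12 months: 21/365 = 5.8%, about 1.8 of 32; shortest possible follow-up about 2.06 years.
- 24 months: 21/730.5 = 2.9%, about 0.9 of 32; shortest possible follow-up about 1.06 years.
- Whole study: 1.9%, about 0.6 of 32; shortest possible follow-up zero.

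All these are upper limits on what can be observed, because they allow for no loss to follow-up. Counting from the end of treatment would lower them. Counting patients treated before July 10, 2017, whom the eligibility criteria do not rule out, would raise them.

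**The case against.** The strongest reply is that the plan never promises 3 years for each patient. In item 6 the words about treatment describe the clinical course, and the bracket is a separate time-frame field that may mean the cohort's observation window. A study of about 3 years with a 3-year window is then consistent, and the near match of the two lengths makes this plausible. The follow-up duration is also labelled a target. This reading is possible, but it amounts to saying that 3 years is a maximum, and the text does not say that. A target follow-up duration is more naturally read as applying to each patient. Even as a window, the plan leaves open how long any patient will be followed and at what time results will be described.

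A second reply is that the percentages rest on stacked assumptions. This is correct. Only the 21-day margin comes directly from the dates. Enrolment to the last day is inferred from two completion dates that coincide, and one date entered in both fields would look the same. The 12-month accrual case shows that early closure of enrolment does not rescue 3 years, although it would make 24 months reachable for everyone. The completion date is an estimate and could be extended, but no section provides for that.

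A third reply is that the plan specifies no 3-year estimate and no last-visit comparison, so neither can be called a planned error. That is fair: both are risks left open by an unspecified analysis. A description over varying follow-up is feasible, provided it is labelled as such. Finally, only one secondary outcome is involved. That limits the reach of the point, but this outcome carries the study's second aim.

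**Conclusion.** The concern holds. On the plan's own dates, a 3-year follow-up can be reached only by patients who start treatment in the first 21 of 1,117 days. This rests on treatment starting within the study, follow-up counted from its start, and completion on July 31, 2020. Across accrual periods from 12 months to the whole study, with uniform starts, about 6% down to 2% of ocular patients could reach 3 years, roughly 2 to fewer than 1 of the expected 32. The margin is firm; the percentages are illustrative because accrual is not stated. The point should be fixed before outcome 6 is reported. The primary outcomes, the other five secondary outcomes and the sample size are untouched.

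**What to change.** Reword item 6 and the target follow-up in both places as up to 3 years from start of treatment, with data cut-off July 31, 2020. State when enrolment closes. Report the distribution of follow-up time in the ocular cohort.

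Describe the clinical course, in whatever measure the investigators define for it, at one fixed time that the calendar supports, and give the number of patients contributing. Twelve months is one example: it would be limited to patients whose treatment started by July 31, 2019, so that eligibility depends on the calendar and not on who happened to stay in follow-up.

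The cost is a change of wording and one extra summary. The stated follow-up becomes less favourable, and late-treated patients drop out of the fixed-time report: about a third at 12 months (1 − 0.672 = 0.328) if starts are uniform to the end. If the sponsor wants 3 years for every patient, the alternative is to extend study completion and the IRB approval to 3 years after the last ocular patient starts treatment, which is a much larger commitment.
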